6.2. Statistical methods

The primary analysis will adhere to the intention to treat principle regardless of treatment deviations made either in error or per the best medical judgment of the treating ophthalmologist. Evaluation of continuous outcomes over time (such as log change in retinal thickness or best corrected visual acuity) and binary outcomes over time (such as normal/abnormal IOP) will use a repeated measures analysis with Gaussian or logit links that account for the nested correlations between observations over time and between eyes of the same patient.⁹⁰ A saturated mean model, including visit and visit by treatment interaction terms, will be used. An unstructured covariance matrix will be used to model the within-eye repeated measurements augmented by random effects to induce cross-sectional between-eye associations. Alternatives, including a first-order, auto-regressive process (an AR(1) model) along with a random intercept, will be considered if the unstructured covariance model is unstable. This structure allows for correlation to decrease with increasing time-separation down to a level set by the random intercept.

Significance for superiority hypotheses in POINT will be determined by comparing the p-value of the interaction term for the week 8 visit with 0.01667 (i.e. 0.05/3). Significance for the non-inferiority hypothesis in POINT will be assessed by comparing the upper bound of the 96.7% confidence intervals for estimate of the difference in change in log retinal thickness at 8 weeks, which is estimated by the 8-week interaction term, with the defined non-inferiority boundary of 0.15 on the log scale, which is equivalent to a 10% difference in percent reduction (40% vs 30% reduction) for the two groups.

Evaluation of risk factors for time-to-event outcomes such as incidence of cataracts, as well as time to remission will be performed using Cox proportional hazards regression as well as parametric time-to-failure models, such as gamma models⁹¹. Implementation of these models that allows for clustering (within patients and within eyes), assessment of recurrent events, and incorporation of time-dependent covariates will be used. When the relevant follow-up time in the analysis reflects the clinical time scale (e.g. time since diagnosis of uveitis), it is necessary to incorporate the prevalent cases (longstanding diagnosis of uveitis) into the analysis. To accommodate the prevalent cases we will use the staggered entry technique⁹², which is one method of adjusting for potential survival bias. The analysis compares the event rates among patients with similar duration of disease and then combines over these comparisons. Event rates for multiple recurring events, e.g. the number of adverse events, will be modeled using Poisson regression or Negative Binomial regression⁹³, including a random effects term to account for the between eye correlation.

All analyses will be performed both unadjusted, except for the stratification variable, and adjusted for potential confounders. Effect modification due to factors such as disease location or uveitis activity, fluorescein leakage in the central subfield, systemic disease, gender and race also will be explored when appropriate. Robust standard errors will be computed using statistical program-based approaches when available and a bootstrap with the individual as the sampling unit, when a pre-programmed approach is not available.

POINT has a focused set of primary research questions and related analyses. Bonferonni corrections will be applied to control the type I error rates for the primary hypotheses within each study. However, a large number of comparisons are planned for secondary outcomes and caution is needed in the reporting of interpretation of the results. Our primary focus for analyses of these outcomes will be on the parameter estimates and confidence intervals as opposed to p-values as recommended by Wang et al⁹⁴. Several methods of adjusting P-values for multiple comparisons exist, however no clear consensus as to the most appropriate method is available and it is difficult if not impossible to quantify ahead of time the number of comparisons that will be performed. In general, issuing cautions is sufficient, but for identifiable and related sets of

estimates we will do adjustments. We expect that related sets of estimates will have a high positive correlation, making a Bonferroni correction extremely conservative. Therefore, we will estimate the covariance matrix for these related sets using a bootstrap approach and also estimate the null distribution of the minimum P-values for the multivariate distribution of Z-scores using a global null hypothesis permutation distribution.

The best protection against bias caused by missing data is to prevent it. We will work with coordinators and participants, as we have done in previous trials, to ensure that missing data are infrequent. Regardless, we will perform a variety of sensitivity analyses to determine the potential for bias due missing data. For a crude estimate of the range of potential impact, 'best' and 'worst' case single imputation techniques will be implement. In addition, more sophisticated approaches (e.g. multiple imputation and pattern mixture) will also be used to assess the impact of missing data^{95, 96}. For the principal sensitivity analysis, we will retain all features of the primary analysis other than how missing values for visits beyond the last one with a measured value are handled. As is implicit in the primary analysis where missing data indicators are used (e.g. "." in SAS, "NA" in R), we will treat all missing values as Missing at Random (MAR). We will impute other missing values to generate 10 pseudo-complete records for each such individual by sampling from a joint predictive distribution for the missing data given the observed data. We will use a covariance matrix equal to the estimated covariance matrix from the primary analysis, but will "take control" of the prediction mean. Varying the mean of the predictive distribution allows us to assess the sensitivity of our results to a variety of missing data scenarios. The pattern mixture model approach stratifies participants on their pattern of missing data, estimates stratum-specific parameters and then combines estimates over strata using inverse variance weights. The approach is similar to stratified analysis to adjust for potential confounders and allows for comparison of stratum-specific estimates. We stratify by three patterns: complete data, at least one internal measurement missing, and closeout weight missing (along with any other missingness).

7. Regulatory and ethical issues

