2.2. Hypothesis

Primary hypotheses:

- (1) Intravitreal triamcinolone injections will have greater efficacy than periocular triamcinolone as a treatment for uveitic macular edema.
- (2) Intravitreal injections of the dexamethasone pellet will have greater efficacy than periocular triamcinolone injections as a treatment for uveitic macular edema.
- (3) Intravitreal injections of the dexamethasone pellet will be non-inferior to intravitreal triamcinolone as a treatment for uveitic macular edema.

Secondary hypothesis:

- (1) Intravitreal injections of the dexamethasone pellet will have a lower rate of IOP elevation than intravitreal triamcinolone injections over the 24 weeks of follow-up.

3. Design

[figure not shown]

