3.5. Secondary outcomes

- Rate of IOP elevation of >21 mm Hg or \geq 10 mm Hg from baseline during the 24 weeks of follow-up
- Percent change in macular thickness as measured by OCT over the 24 weeks of follow-up
- Proportion of eyes with macular edema events over the 24 weeks of follow-up
 - \geq 20% reduction in macular thickness (or normalization of macular thickness even if there is <20% reduction)
 - "Resolution", defined as normalization of the macular thickness to within \pm 2 standard deviations of the normative mean for the OCT machine used
 - Worsening defined as a 20% increase in macular thickness from the lowest value after an injection
 - "Recurrence" defined as >20% increase in the central subfield measurement on OCT to an abnormal value in an eye that previously had resolution of ME
- Mean change in BCVA over the 24 weeks of follow-up.
Best-corrected visual acuity score will be measured at every study visit under standardized lighting conditions by certified study examiners masked to study treatment using logarithmic (ETDRS) visual acuity charts, according to the method described by Ferris, et al.⁷⁵
- Inflammation as graded using the semi quantitative scales used in the MUST Trial i.e., clinician grading of the presence and extent of anterior chamber cells, anterior vitreous cells, and vitreous haze based on previously published standard ordinal scales (0, trace, 1+, 2+, 3+, 4+)⁷⁶⁻⁷⁸ using the scales endorsed by the Standardization of Uveitis Nomenclature Working Group when applicable⁷⁹
- Safety outcomes including elevated IOP (>30 mm Hg thresholds); new onset posterior subcapsular (PSC) cataract or progression of pre-existing PSC (using the Age-Related Eye Disease Study [AREDS] scheme⁸⁰; vitreous hemorrhage; retinal tear/detachment; endophthalmitis; severe vision loss (\geq 15 Early Treatment Diabetic Retinopathy Study [ETDRS] letters) during the 24 weeks of follow-up.
- Cost-effectiveness of treatments for uveitic macular edema during the 24 weeks of follow-up will be assessed by enumerating costs of treatments and procedures for uveitis during the 24 week follow-up; participants' utilities will be measure with the EuroQol questionnaire.
- Visual function related quality of life as measured by the NEI Visual Function Questionnaire (25 item version).

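### Does the plan fail to say which analysis answers its one secondary hypothesis, the rate of IOP elevation over 24 weeks?

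*Combined protocol and SAP*

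**What the plan says.** Section 2.2 lists one secondary hypothesis: the dexamethasone pellet "will have a lower rate of IOP elevation than intravitreal triamcinolone injections over the 24 weeks of follow-up". Section 3.5 defines the outcome as "Rate of IOP elevation of >21 mm Hg or" a rise of at least 10 mm Hg from baseline, counted during the same 24 weeks. Section 6.1 treats it as an important secondary outcome. It powers the outcome as a percentage of eyes, 12% on dexamethasone against 40% on intravitreal triamcinolone, with 89 independent eyes per arm and a two-sided 0.05 level, and states 99% power.

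Section 6.2 covers the analysis in general terms:

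- Repeated outcomes: "binary outcomes over time (such as normal/abnormal IOP) will use a repeated measures analysis with Gaussian or logit links". On the mean structure: "A saturated mean model, including visit and visit by treatment interaction terms, will be used". A deciding term, the week-8 interaction, is named only for the three thickness hypotheses.
- Time-to-event outcomes: Cox or parametric models, with cataract and remission as examples. "Implementation of these models that allows for clustering (within patients and within eyes), assessment of recurrent events" is provided for.
- Recurring events: Poisson or negative binomial models, with adverse-event counts as the example.
- Standard errors: robust where the software provides them, otherwise "a bootstrap with the individual as the sampling unit".
- Secondary outcomes generally: "Our primary focus for analyses of these outcomes will be on the parameter estimates and confidence intervals as opposed to p-values".

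Section 3.8 schedules tonometry at baseline and at weeks 4, 8, 12, 20 and 24.

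**The concern.** A hypothesis about a rate over 24 weeks is naturally read as how many eyes ever have an elevation, or how often. The only method in section 6.2 that mentions IOP estimates something else, namely the share of eyes with abnormal pressure at each of five visits. The two can differ. Section 1.6 says that pressure rises after intravitreal triamcinolone are mostly transient and can be controlled with medication. The outcome in section 3.5 counts pressure only, so a treated eye that is back in range scores as normal at later visits.

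The time-to-event and event-rate models in section 6.2 could also apply, but neither is assigned to IOP. Visit-specific prevalence, first occurrence and recurrent rate are three different quantities, and each could be reported as the answer. At stake is a choice made after the data are seen, on the only stated secondary hypothesis. If the choice fell on a single late visit, a true difference could be understated.

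**Working it through.** **1. Reproduce the plan's power.** Inputs from section 6.1: n = 89 eyes per arm, p1 = 0.12, p2 = 0.40, two-sided 0.05.

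- Mean proportion: (0.12 + 0.40)/2 = 0.26.
- Null standard error: sqrt(2 × 0.26 × 0.74/89) = 0.0658.
- Alternative standard error: sqrt((0.12 × 0.88 + 0.40 × 0.60)/89) = 0.0623.
- Power: Φ[(0.28 − 1.96 × 0.0658)/0.0623] = 0.992. Fisher's exact test gives 0.989.

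The equation of 89 eyes with 89 patients also holds. The section 6.1 factor is 1.4/(2 × 0.25 + 1.4 × 0.75) = 0.903, and 89 × 0.903/0.90 = 89.3. The stated 99% is correct, and it is the power of one comparison of two proportions of eyes.

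**2. See what is already fixed.**

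| Element | Where stated |
|---|---|
| Arms and direction | 2.2 |
| 24-week window | 2.2 and 3.5 |
| Pressure threshold | 3.5 |
| Measure: percent of eyes | 6.1 |
| Two-sided 0.05 | 6.1 |
| Handling of paired eyes | 6.2 (models for clustered data, robust errors, bootstrap by individual) |
| Missing data | 6.2 (best and worst "case single imputation techniques will be implement", plus multiple imputation) |
| Which estimate answers the hypothesis | not stated |

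Only the last row is open. Read together, the other rows point to the proportion of study eyes with any qualifying elevation by week 24.

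**3. Size the worst reading.** Suppose 12% and 40% are occurrence by week 24, and a share of affected eyes, equal in both arms, is back in range at the visit tested. The documents do not give that share, so a range is shown, using the formula in step 1.

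| Back in range | Rates at the visit | Power, one visit |
|---|---|---|
| 0% | 12 v 40 | 99% |
| 25% | 9 v 30 | 95% |
| 50% | 6 v 20 | 80% |
| 75% | 3 v 10 | 47% |

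These losses require a test at a single visit, which no section proposes for IOP.

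**4. Use the by-visit model over the whole period.** The same saturated model supports a contrast averaged over the five post-baseline visits, which fits a hypothesis about the whole of follow-up. As a simple stand-in for the logit model, compare each eye's fraction of elevated visits. Let s be the chance that an affected eye is elevated at a given visit, independent across visits. The mean per eye is p × s, and the variance is p × e − (p × s)², where e = s(1 − s)/5 + s².

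For s = 0.5:

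- e = 0.05 + 0.25 = 0.30.
- Variances: 0.40 × 0.30 − 0.20² = 0.080 and 0.12 × 0.30 − 0.06² = 0.0324.
- Standard error: sqrt(0.1124/89) = 0.0355. Difference: 0.28 × 0.5 = 0.14.
- z = 0.14/0.0355 = 3.94, and power = Φ(3.94 − 1.96) = 0.98.

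The same steps give z = 4.28 and power 0.99 for s = 0.75, and z = 3.26 and power 0.90 for s = 0.25 (0.91 by simulation). In the last case 0.75⁵ = 24% of affected eyes show no elevation at any visit, so that row is severe. Transience alone therefore does little harm to the by-visit model unless one visit is singled out.

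**The case for a change.** The strongest case for a change is that this is the only stated secondary hypothesis, it has its own power statement, and the one model that mentions IOP does not directly produce the powered quantity. A preference for estimates over p-values makes it more important, not less, to know which estimate is meant, because an odds ratio at a visit, a hazard ratio and a rate ratio are not interchangeable. One sentence would settle it, using tools already in section 6.2.

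What stands is that the sentence is missing. Three things weaken the case for requiring it.

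- IOP appears in section 6.2 as an example of a type of outcome. The example lists for incidence and event-rate models are open too, so nothing bars the analyst from comparing proportions of eyes.
- The evidence that the readings diverge is thin. In section 1.6, the 7.1% peak for the 0.7 mg implant is at 25 mm Hg or more, and the figure of up to 23% of eyes is medication use. Neither is the section 3.5 threshold. The remark about transience concerns triamcinolone, whereas the illustration in step 3 applies one share to both arms.
- The choice between a simple proportion, time to first elevation and an average over visits is partly taste. A time-to-event model would know onset only to the nearest visit, and it would lead with a ratio although section 6.1 powers a difference in proportions.

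Two side points add nothing. Section 6.1 opens with a looser name for the outcome but within the same paragraph gives it as a percentage of eyes. Its 12% does not contradict the 20%-or-more-of-patients heading in section 4.4.3, which has no threshold or window and counts patients, not eyes.

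**Conclusion.** No change to the plan is needed. Section 6.2 leaves one choice unwritten: which estimate answers the IOP hypothesis. The arms, direction, window, threshold, measure and error level are all stated elsewhere, and a sensible analyst would fill the gap with the proportion of eyes elevated by week 24, allowing for paired eyes, with the by-visit results alongside. For that quantity the stated 99% power is right at 12% versus 40%.

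The large power losses (down to 47%) belong to a single-visit test that the plan does not propose for IOP. A contrast averaged over visits keeps about 90% or more across the range examined. Those figures assume equal shares back in range in both arms, independence across visits within affected eyes, and 89 independent eyes per arm. The thickness hypotheses are untouched, and secondary outcomes are to be read mainly through estimates and intervals, so the consequence is small.

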3.6. Eligibility criteria

Inclusion criteria:

Patient level inclusion criterion:

1. 18 years of age or older;

Eye level inclusion criteria - at least one eye must meet all of the following conditions

2. Non-infectious anterior, intermediate, posterior or panuveitis; either active or inactive uveitis is acceptable;
3. Macular edema (ME) defined as the presence of central subfield macular thickness greater than the normal range for the OCT machine being used ($>300\ \mu\text{m}$ for Zeiss Cirrus/Topcon 3DOCT or $>320\ \mu\text{m}$ for Heidelberg Spectralis), regardless of the presence of cysts, as assessed by study ophthalmologist;
4. Best corrected visual acuity (BCVA) 5/200 or better;
5. Baseline intraocular pressure $> 5\ \text{mm Hg}$ and $\leq 21\ \text{mm Hg}$ (current use of 3 or fewer intraocular pressure-lowering medications and/or prior glaucoma surgery are acceptable – *note that combination medications, i.e., Cosopt, count as 2 IOP lowering medications*);
6. Baseline fluorescein angiogram that is gradable for degree of leakage in the central subfield
7. Pupillary dilation sufficient to allow OCT testing.

Exclusion criteria:

Patient level exclusion criteria:

1. History of infectious endophthalmitis or infectious uveitis in either eye;
2. History of infectious scleritis of any type in either eye. (*Note: History of noninfectious scleritis that has been active in past 12 months is an eye-level exclusion –see #11 below.*)
3. History of keratitis (with the exception of keratitis due to dry eye) in either eye;
4. History of central serous retinopathy in either eye;
5. For women of childbearing potential: pregnancy, breastfeeding, or a positive pregnancy test; unwilling to practice an adequate birth control method (abstinence, combination barrier and spermicide, or hormonal) for duration of trial;
6. Use of oral acetazolamide or other systemic carbonic anhydrase inhibitor at baseline;
7. Oral prednisone dose $> 10\ \text{mg}$ per day (or of an alternative corticosteroid at a dose higher than that equipotent to prednisone $10\ \text{mg}$ per day) OR oral prednisone dose $\leq 10\ \text{mg}$ per day at baseline that has not been stable for at least 4 weeks (*note that if patient is off of oral prednisone at baseline (P01 visit), dose stability requirement for past 4 weeks does not apply*);

8. Systemic immunosuppressive drug therapy that has not been stable for at least 4 weeks;

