Power calculations for the primary hypotheses are based upon pair-wise comparisons of the three treatment arms: intravitreal injection of triamcinolone, dexamethasone pellet, and periocular injection of triamcinolone. A Bonferroni correction will be used to adjust for multiple comparisons, i.e. a two-sided type I error rate of $0.05/3 = 0.01667$ will be used to determine statistical significance. The sample sizes needed to provide 90% power for the superiority hypotheses (intravitreal injection or dexamethasone pellet versus periocular injection) and 80% power for the non-inferiority hypothesis (intravitreal injection versus dexamethasone pellet) were computed separately for each comparison and then the maximum sample size was selected. The primary outcome is the change in retinal thickness at the central subfield at 8 weeks. Given the skewness in the distribution of retinal thickness, a log-transformation will be used to analyze the primary outcome^{74, 87}; hence, the comparisons will be represented on a relative scale (i.e. percent of baseline) and transformed to obtain the percent change from baseline. A 20% change in retinal thickness is associated with clinically meaningful changes in visual acuity.⁷⁴ In the MUST Trial, approximately 25% of individuals had bilateral macular edema and the correlation between-eyes was 0.40 for log retinal thickness.^{4, 6} The standard deviation for change in log retinal thickness was approximately 0.33 in the MUST Trial; a conservative estimate since the treatment of macular edema was not standardized and the timing of the assessment, at 6 months after randomization, was not linked to the implementation of treatment for macular edema. Based upon the 6-month OCT evaluation in the MUST Trial, we allowed for a 10% loss to follow-up.

For the first two superiority hypotheses, we evaluated the power to show that each of the treatment methods for intravitreal corticosteroids (triamcinolone injections and dexamethasone pellets) is superior to periocular triamcinolone injections at 8 weeks. In previous studies, treatment with the dexamethasone pellet has resulted in a decrease in retinal thickness of 30%-

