For the third hypothesis, we evaluated the power to show that the dexamethasone pellet is non-inferior to injected triamcinolone. Previous research has indicated that the threshold for reproducibility is 10% and that a 20% change is associated with changes in visual acuity.^{74, 88} Therefore, we chose a non-inferiority margin of 10%, i.e. we would consider the dexamethasone pellet to be non-inferior if the percent reduction in retinal thickness was 30% or more ($\log[0.7]$) as opposed to a 40% ($\log[0.60]$) in the intravitreal injection group, i.e. the difference in the log retinal change was at most 0.15 ($\log[0.7] - \log[0.6]$). A sample size of 89 independent eyes per treatment group will provide 80% power to demonstrate non-inferiority with a one-sided type I error rate of 0.01667. We would reject the null hypothesis of inferiority if the upper bound of the 96.7% confidence interval of the difference in log retinal change from baseline at 8 weeks was less than 0.15 ($\log[0.7] - \log[0.6]$) or equivalently if the ratio of the percent of baseline for the two groups was less than 1.16 (0.7/0.6). Assuming a between-eye correlation of 0.4, 25% bilateral disease, and a 10% loss to follow-up, we will need to enroll 89 individuals in each treatment arm to attain 80% power, i.e. the inclusion of both eyes for bilateral disease off-sets the sample size inflation necessary to account for losses to follow-up.

An important secondary outcome for the comparison of intravitreal triamcinolone injection versus the dexamethasone pellet will be change in IOP. In prior studies, treatment with intravitreal triamcinolone resulted in IOP elevation for 40% of study eyes.^{33, 51} In contrast, reports of IOP elevation with dexamethasone pellet have been more variable but consistently lower, ranging from 5% to 17%.^{62, 68} A sample size of 89 independent eyes per treatment group, which is equivalent to 89 individuals per arm allowing for bilateral disease and losses to follow-up, will provide 99% power to detect an increase in the percent of eyes with an IOP elevation from 12% in the dexamethasone pellet arm to 40% in the intravitreal triamcinolone injection arm with a 2-sided, type I error rate of 0.05.

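### As most naturally read, the deciding week-8 contrast is not adjusted for baseline thickness; adjusting it could raise non-inferiority power with no extra patients

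*Combined protocol and SAP*

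**What the plan says.** Section 6.2 introduces the model with "Evaluation of continuous outcomes over time (such as log change in retinal thickness or best corrected visual acuity" and specifies the mean structure as "A saturated mean model, including visit and visit by treatment interaction terms, will be used". Superiority is judged on the p-value of the week-8 interaction. Non-inferiority is judged on the upper confidence bound for "the difference in change in log retinal thickness at 8 weeks, which is estimated by the 8-week interaction term". Section 6.2 adds: "All analyses will be performed both unadjusted, except for the stratification variable, and adjusted for potential confounders". It does not list the confounders or say which version decides.

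Section 6.1 bases power on the SD of change in log thickness, 0.33, described as "a conservative estimate since the treatment of macular edema was not standardized". It states "80% power to demonstrate non-inferiority with a one-sided type I error rate of 0.01667" with 89 independent eyes per arm.

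Neither section names baseline thickness as a covariate or states that baseline means are held equal across arms. Section 3.8 schedules OCT at baseline and at five later visits.

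**The concern.** If log change is the response at the five post-baseline visits, visit plus visit-by-treatment is already the saturated mean. Its week-8 term is then the difference between arms in mean change, with no adjustment for baseline thickness. An unstructured covariance does not supply that adjustment.

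This matters most for non-inferiority, which has the least slack of the three hypotheses. At SD 0.33 the implant passes only if the observed log difference is below about 0.045.

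The documents also suggest that change depends on where an eye starts. Section 3.6 requires "presence of central subfield macular thickness greater than the normal range for the OCT machine being used", set at 300 or 320 µm depending on the device. Section 3.5 counts as a response "normalization of macular thickness even if there is <20% reduction". Reaching 300 µm takes a fall of 3% from 310 µm, 25% from 400, 40% from 500 and 50% from 600, so thicker eyes have more room to fall. The documents do not say how strong this dependence is.

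**Working it through.** **Inputs from the documents.** 89 independent eyes per arm; SD of change 0.33; non-inferiority margin 0.15 on the log scale; true difference 0 for implant against intravitreal triamcinolone; one-sided 0.01667 (z = 2.128) for non-inferiority; two-sided 0.01667 (z = 2.394) for superiority, 40% against 25% reduction (Sections 6.1 and 6.2).

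**Assumed, because the documents do not give them.** The correlation ρ between baseline and week-8 log thickness, and the SDs s0 (baseline) and s1 (week 8).

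**1. The plan's own figures.** SE = 0.33 × √(2/89) = 0.0495.
- Non-inferiority: Φ(0.15/0.0495 − 2.128) = 81.7%, against 80% stated.
- Superiority: Φ(log(0.75/0.60)/0.0495 − 2.394) = 98.3%, against 98% stated.
- Largest observed difference that still passes non-inferiority: 0.15 − 2.128 × 0.0495 = 0.045, a ratio of 1.046.

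**2. Does the planned model adjust by itself?** Generalised least squares with known covariance, baseline plus five visits, 89 eyes per arm, equal SDs. Week-8 SE:

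| Model | ρ = 0.3 | ρ = 0.5 | ρ = 0.7 |
|---|---|---|---|
| Log change; visit + visit-by-treatment | 0.0495 | 0.0495 | 0.0495 |
| Log thickness; with treatment main effect | 0.0495 | 0.0495 | 0.0495 |
| Log thickness; no treatment main effect (baseline means equal) | 0.0399 | 0.0428 | 0.0456 |

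The first two rows equal the plain change-score SE whatever ρ is. Only the third contains the gain.

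**3. Effect of adjustment.** The variance is multiplied by v = (1 − ρ²)s1² / (s0² + s1² − 2ρ·s0·s1), which equals 1 − corr(change, baseline)² and so cannot exceed 1. With equal SDs, v = (1 + ρ)/2. Power is Φ(0.15/(SE·√v) − 2.128). At ρ = 0.5, v = 0.75, and power is Φ(0.15/0.0428 − 2.128) = 91.5%; this matches 89/0.75 ≈ 119 unadjusted eyes per arm.

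| Setting | Unadjusted | Adjusted |
|---|---|---|
| SD 0.33, equal visit SDs, ρ = 0.3 / 0.5 / 0.7 / 0.9 | 81.7% | 94.9 / 91.5 / 87.7 / 83.7% |
| SD 0.33, s1 = 1.25·s0, ρ = 0.3 / 0.5 / 0.7 / 0.8 | 81.7% | 90.2 / 86.0 / 82.5 / 81.7% |
| SD 0.30 (assumed), equal visit SDs, ρ = 0.3 / 0.5 / 0.7 | 88.6% | 97.8 / 95.8 / 93.2% |
| SD 0.28 (assumed), equal visit SDs, ρ = 0.3 / 0.5 / 0.7 | 92.6% | 98.9 / 97.7 / 96.0% |

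With s1 = 1.25·s0 and ρ = 0.8, the slope of week 8 on baseline is 1.25 × 0.8 = 1. Change is then unrelated to baseline and there is no gain. Superiority rises from 98.3% to at most 99.9% with equal SDs.

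**4. Simulation.** 4,000 trials per setting (Monte Carlo SE about 0.6 points): three arms of 89 patients, 25% bilateral, between-eye correlation 0.4, 10% loss, stratum split 50:50 (assumed), patient random intercept. Week-8 log change was regressed on arm and stratum, without and with log baseline.

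| Setting | Unadjusted | Adjusted |
|---|---|---|
| Equal SDs, ρ = 0.3 | 82.2% | 94.8% |
| Equal SDs, ρ = 0.5 | 80.9% | 91.3% |
| Equal SDs, ρ = 0.7 | 81.1% | 87.7% |
| SD ratio 1.25, ρ = 0.5 | 82.5% | 86.6% |
| SD ratio 1.25, ρ = 0.8 | 82.4% | 82.5% |

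One-sided error at the margin was 1.65% unadjusted and 1.68% adjusted, against 1.667% nominal. This is a week-8 regression, not the full repeated-measures model.

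With equal SDs and no true difference, the two tests gave different non-inferiority verdicts in 13.7%, 12.6% and 8.9% of trials (ρ = 0.3, 0.5, 0.7). In 13.2%, 11.5% and 7.8% only the adjusted test passed, so this mostly restates the power gain.

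**The case against.** The strongest reply is that the gain may already be in the plan. The term list in Section 6.2 has no treatment main effect. The same model is applied to visual acuity, which is named as a level rather than a change. Section 6 promises to analyse everyone randomised, which fits keeping baseline as a response visit. Taken literally with log thickness as the response, those terms hold baseline means equal, and nothing is lost. This reading is possible, but such a model is not saturated, and it does not fit log change as the named outcome. The text does not settle the matter.

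Other points also stand in part:
- The plan meets its own power targets, so this is a refinement and not a correction.
- The size of the gain rests on ρ and visit SDs that the documents do not give.
- If 0.33 is conservative, the unadjusted test already has more room: the passing limit is 0.054 at SD 0.30 and 0.061 at SD 0.28.
- The promised adjusted analysis might include baseline thickness, but it is neither specified nor named as deciding.
- The simulation did not test the unstructured covariance with the added baseline slopes.

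None of this makes adjustment unhelpful. The variance factor cannot exceed 1, and the cost is about one degree of freedom at week 8.

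**Conclusion.** The concern holds, conditional on the unadjusted reading. The planned contrast is valid and its stated power reproduces, but it does not use a baseline measurement that every eligible eye already has. With the planning SD and 89 independent eyes per arm, adjustment moves non-inferiority power from 81.7% to between 83.7% and 94.9% for ρ from 0.9 down to 0.3 with equal visit SDs. It moves it to between 81.7% and 90.2% for ρ from 0.8 down to 0.3 if the week-8 SD is 1.25 times the baseline SD. Superiority is little affected. Under the equal-baseline-means reading there is no further gain, and only the wording needs settling. Confidence is medium, because the documents fix neither the reading nor the correlation.

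**What to change.** State in Section 6.2 that the deciding week-8 model is baseline-adjusted, in one of two forms:
- (a) log change, or post-baseline log thickness, on treatment-by-visit, log baseline thickness-by-visit and the randomisation stratum; or
- (b) log thickness with baseline as a response visit and its mean held equal across arms.

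The two differ slightly for eyes with only a baseline OCT, which (b) retains. Keep the planned covariance structure and report the unadjusted change contrast as a sensitivity analysis. If (b) was meant all along, say so and stop calling the mean model saturated. Also state which of the two promised versions, unadjusted or adjusted, decides the primary hypotheses, and list the confounders.

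The cost is SAP wording. Form (a) adds five slopes over the five post-baseline visits. The estimand (the ratio of percent-of-baseline at 8 weeks), the margin and the sample size do not change. Because the trial is open-label and the Coordinating Center prepares monitoring reports with outcomes by assigned arm (Section 7.2.4), the choice should be made and dated without reference to arm-level outcome data.
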